Secondary Objectives	 To characterize the preliminary safety and tolerability of K-MaP in demoralized patients with stage 3 and 4 GI cancers. To assess the magnitude and durability of improvement from randomization in psychosocial distress. To assess the magnitude and durability of improvement from randomization in pain. To assess the magnitude of change from randomization in opioid analgesic use. To assess the magnitude and durability of change from randomization in interoceptive awareness. 							
Sample Size	12 patients, 6 patients per arm. Arm A: (0.5 mg/kg of ketamine, PO) Arm B: (0.5 mg/kg of ketamine, IM)							
Duration of Study Treatment	Ketamine will be given once on Day 0/Visit 4. Patients will receive MaP therapy 4 times, twice before ketamine administration (Day 0), and twice afterward: 1. Day -13 to -4/Visit 2 2. Day -12 to -1/Visit 3 3. Day 3 (+/- 2 days)/Visit 5 4. Day 11 (+/-2 days)/Visit 7 The duration of treatment for K-MaP therapy (ketamine and MaP) is approximately up to 28 days.							
Duration of Follow up	Patients will be followed up to 35 days (+/-2 days) after ketamine administration.							

Pilot Study - Ketamine Page 4 of 55

Study Schema

Pilot Study - Ketamine Page 5 of 55

List of Abbreviations

AE adverse event

ALP alkaline phosphatase

ALT alanine aminotransferase
AST aspartate aminotransferase

BMP Basic Metabolic Panel

BPI-SF Brief Pain Inventory-Short Form

BUN blood urea nitrogen

CBC complete blood cell (count)

CEQ Challenging Experience Questionnaire

CMP Comprehensive Metabolic Panel

CNS central nervous system

CR complete response

CRF case report form

C-SSRS Columbia Suicidality Severity Rating Scale

CT computerized tomography

CTCAE Common Terminology Criteria for Adverse Events

CTMS Clinical Trial Management System

DFS disease-free survival
DLT Dose-limiting toxicity
DS-II Demoralization Scale II

DSMC Data and Safety Monitoring Committee

DSMP Data and Safety Monitoring Plan

ECG/EKG electrocardiogram

ECOG Eastern Cooperative Oncology Group

FACIT- Functional Assessment of Chronic Illness Therapy Palliative Care 14 Item Version

Pal-14

FDA Food and Drug Administration

FDG Fluorodeoxyglucose

GAD7 General Anxiety Disorder-7

GCP Good Clinical Practice
GFR glomerular filtration rate

HBsAb hepatitis B surface antibody HBsAg hepatitis B surface antigen HBcAb hepatitis B core antibody

HC Ab hepatitis C antibody

Pilot Study - Ketamine Page 6 of 55

List of Abbreviations

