1.2 Background on the Investigational Product(s) and Associated Known Toxicities

Ketamine is a centrally-acting NMDA glutamate receptor antagonist that is a DEA Schedule 3 medicine and FDA-approved as a dissociative anesthetic. Esketamine (the s-stereoisomer of

Pilot Study - Ketamine Page 10 of 55

ketamine) was approved by the FDA in 2019 for treatment-resistant depression. Ketamine is used widely for procedural sedation and is frequently used off-label for chronic pain and psychiatric disorders, including depression and anxiety. The use of ketamine for treatment of depression is supported by specialty medical societies including the American Psychiatric Society and the American Society of Ketamine Physicians, Psychotherapists, and Practitioners. The UCSF Lexicomp label lists depression as an indication for ketamine. Ketamine therapy for psychiatric illness is offered widely in California, including by the SF Veterans Administration Medical Center, UCLA, and UCSD. The UCSF P&T committee approved use of ketamine for depression in June 2018.

This section of text is excerpted from the UCSF UpToDate Lexicomp on Ketamine:[44]

Ketamine is a racemic mixture of two enantiomers, S-ketamine and R-ketamine. Ketamine is a standard anesthetic drug that is also administered for analgesia and sedation [2,3]. In addition, ketamine and esketamine can rapidly and transiently alleviate treatment-resistant unipolar major depression, including suicidal ideation [4,5]. For unipolar major depression, the efficacy of ketamine and esketamine appear to be comparable [1]. However, no head-to-head trials comparing the two drugs have been published.

The optimal method of administering ketamine for treatment resistant depression has not been established [26]. Although most studies have given ketamine intravenously, it can also be administered with intramuscular, intranasal, oral, subcutaneous, and sublingual formulations [2,12,25,27-29].

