We will test two different doses and routes of ketamine administration: 0.5mg/kg PO and 0.5mg/kg IM. These doses were selected on the basis of existing data. As a safety precaution, we will use a maximum limit of oral ketamine of 60 mg, given that higher doses have not been evaluated in clinical trial settings in the U.S.

Case series and one published clinical trial of oral ketamine as a treatment of depression in patients with advanced cancer have shown that a daily oral dose of 0.5mg/kg is well-tolerated and briefly improved depression symptoms [55-57]. An ongoing trial of weekly oral ketamine for anxiety in patients with pancreatic ductal adenocarcinoma (PDAC) is using a dose of 0.5mg/kg PO [58]. The bioavailability of oral ketamine is estimated to be 10-17% [59].

Clinical trials investigating the use of intramuscular ketamine for the treatment of depression in palliative populations and the general public have used starting doses ranging from 0.1mg/kg -1.0mg/kg IM [60-62], all of which have been reported to be relatively well-tolerated. The bioavailability of intramuscular ketamine is 93% [63, 64]. Similar or higher doses of ketamine are frequently used in various clinical settings. Many trials of IV ketamine for unipolar depression have used a dose of 0.5mg/kg administered as a slow infusion [65], while one survey of n=98 community clinics administering off-label ketamine for psychiatric conditions uses doses ranging from 0.5-3.0mg/kg IV [66]. A retrospective study of n=420 patients receiving IM ketamine for depression found starting doses ranging from 0.3 - 2.15mg/kg IM, with a median starting dose of 0.55mg/kg IM [67]. A second case series of n = 40 patients utilized a protocol involving a starting dose of ketamine 1.0mg/kg IM, divided into two 0.5m/kg IM doses spaced 15 minutes apart [68]. In a recent systematic review of ketamine in palliative care populations, patients were most commonly started at starting doses of ketamine 0.5mg/kg SC or IV [69]. Another survey of three ketamine clinics (two of which are in the San Francisco Bay Area) provided data on n=253 patients treated with off-label ketamine-assisted psychotherapy using sublingual administration (with a bioavailability of 15-25%) at doses of 25-400 mg, and often in the range of 200-250 mg [70]. Finally, in an FDA-related abuse liability study published in 2011, 100 mg of oral ketamine was used as a control drug for the serotonin 2C receptor agonist lorcaserin [71].

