9.1 Sample Size Considerations

9.1.1 Sample Size and Power Estimate

No formal power analysis was conducted, and no formal tests of efficacy will be conducted. This N=12 pilot study has a sample size sufficient for assessing the feasibility and preliminary safety of a novel behavioral-pharmaceutical intervention, at two different dose levels and routes of administration of the study drug.

If the 0.5mg/kg PO dose of ketamine is well-tolerated (i.e., zero treatment-related SAEs) and demonstrates mean clinical improvement in demoralization assessed by DS-II that endures beyond 7 days post-drug, then this would suggest a fully powered study is warranted using the 0.5mg/kg PO dose.

If the 0.5mg/kg IM dose of ketamine is well-tolerated (i.e., zero treatment-related SAEs) and demonstrates mean clinical improvement in demoralization assessed by DS-II that endures beyond 7 days post-drug, then this would suggest a fully powered study is warranted using the 0.5mg/kg IM dose.

If the either dose is well-tolerated and fails to demonstrate mean clinical improvement in demoralization assessed by DS-II that endures beyond 7 days post-drug, then this would suggest that the dose is an appropriate control for other psychoactive investigational drugs whose clinical effects are expected to have greater durability.

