Secondary Objective #2: To assess the magnitude and durability of improvement from randomization in psychosocial distress associated with K-MaP, we will measure mean trends in patient-reported outcomes (DS-II, PHQ9, GAD7, FACIT-PAL-14 scores) in each study arm from baseline visit (Day -28 to -7) to post-ketamine (on Days 7, 14, and 35). In addition, we will calculate the proportion of participants per arm who no longer meet criteria for moderate-to-severe demoralization (i.e., DS-II > 10) post-ketamine. We will also measure mean trends in clinician-rated outcomes (CGI-S, DI, and GRID-HAMD-6 scores) per arm as above. ANCOVA models of follow-up endpoints as a function of study arm, adjusted for endpoints at baseline and randomization, will be conducted [110]. ANCOVA results will be presented graphically via mean trends per arm overlaid on individual trends, and via the mean (95% CI) difference between arms at Day 35. Cohen's d will be calculated at each follow-up time to estimate effect sizes. Any missing data will be estimated through the use of single imputation with baseline observations carried forward.

Secondary Objective #3: We will evaluate BPI-SF scores analogously to DS-II scores.

Secondary Objective #4: We will evaluate opioid analgesia use analogously to DS-II scores.

Secondary Objective #5: We will be using pair t-tests to measure mean changes in MAIA-2 scores in each study arm from prior to ketamine administration (on Day 0) to post-ketamine (on Day 7).

Secondary Objective #6: To assess how participants' subjective experiences with ketamine may be related to clinical outcomes, subjective reports of each participant's ketamine experience (videorecorded from Day 0) will be transcribed, inductively coded, and qualitatively analyzed to identify phenomenological content. In addition, participant MEQ and CEQ scores, which provide summary measures of the intensity of ketamine's acute effects, will be evaluated for potential correlation with trends in DS-II, BPI-SF, and opioid use.

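### The durability rule rests on each arm's mean DS-II improvement beyond 7 days, but the plan gives no confidence interval for that change at any visit; its only interval for these outcomes is a between-arm difference at Day 35, which the rule does not use.

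*Combined protocol and SAP*

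**What the plan says.** The Abstract gives the sample size as "12 patients, 6 patients per arm" and names a DS-II fall of 2 points as the smallest change to be taken as a sign of efficacy. Section 6 and the Study Calendar place the post-dose DS-II at Days 7, 14 and 35, each with a window of 2 days either side.

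Section 9.1.1 states that "No formal power analysis was conducted, and no formal tests of efficacy will be conducted". It then sets a rule for the oral and the intramuscular dose separately. A fully powered study is suggested if the arm has no treatment-related serious adverse event and "demonstrates mean clinical improvement in demoralization assessed by DS-II that endures beyond 7 days post-drug". If a tolerated dose does not show this, the conclusion is that "the dose is an appropriate control for other psychoactive investigational drugs whose clinical effects are expected to have greater durability". The section does not name the visit or visits at which durability is read, and does not mention the 2-point minimum.

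For Secondary Objective #2, Section 9.2.3 plans mean trends per arm, ANCOVA of the follow-up values on arm with adjustment for the baseline and randomization values, plots of arm means over individual courses, and Cohen's d at each follow-up time. The only interval is for the ANCOVA contrast, presented "via the mean (95% CI) difference between arms at Day 35". Pain and opioid use are to be handled in the same way. The trends are described as starting at the baseline visit (Day -28 to -7), although the objective is improvement from randomization, which is Day 0.

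**The concern.** The rule and the planned interval concern different quantities. The rule asks whether one arm improved and stayed improved. The interval says how far apart the two arms are. A between-arm difference near zero fits two arms that both improved by several points as well as two arms that did not change. Even at Day 35, the planned interval cannot show how certain an arm's own improvement is.

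The rule has consequences on both sides: it can support a larger trial of a dose, or class that dose as a control for other drugs. As written, either conclusion would be drawn from a mean of six patients with no stated uncertainty.

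The starting point adds to the problem. Two therapy sessions take place between the baseline visit and Day 0. A change counted from the baseline visit includes whatever those sessions achieved; a change counted from Day 0 does not.

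**Working it through.** The plan states no power, no SD and no precision target, so there is no figure of its own to reproduce. The check is of precision only.

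**Inputs.** 6 patients per arm (Abstract); minimum meaningful change of 2 DS-II points (Abstract); ANCOVA with arm, baseline value and randomization value as terms (Section 9.2.3). The SD of DS-II change is an assumption: 4 to 5 points as the main case, up to 8 as a wider range. Complete data are assumed.

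**1. Interval for one arm's mean change (the quantity in the rule).** Half-width = t(0.975, 5 df) × SD / √6 = 2.571 × SD / 2.449 = 1.05 SD.

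| Assumed SD | Half-width (points) | Multiple of 2 points |
|---|---|---|
| 4 | 4.2 | 2.1 |
| 5 | 5.2 | 2.6 |
| 6 | 6.3 | 3.2 |
| 8 | 8.4 | 4.2 |

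For example, an observed mean fall of 3 points with SD 4 has a 95% interval from 3 − 4.2 = −1.2 to 3 + 4.2 = 7.2. That range includes no change at all and more than three times the minimum.

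**2. Chance of misreading a bare mean.** With no true change, P(observed mean fall ≥ 2) = 1 − Φ(2 / (SD/√6)). This is 0.11 for SD 4, 0.16 for SD 5, 0.21 for SD 6 and 0.27 for SD 8, per arm and per visit. By symmetry, an arm with a true mean fall of 4 points would show less than 2 with the same probabilities. The error can go either way.

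**3. Effect of leaving the visit and threshold open.** With no true change and SD 4 to 5:

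| Reading of the rule | Probability of passing by chance |
|---|---|
| Fall of at least 2 points at one visit | 0.11 to 0.16 |
| Fall of at least 2 points at both Day 14 and Day 35 | 0.04 to 0.10 |
| Any fall at one visit | 0.50 |
| Any fall at both visits | 0.33 to 0.40 |

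The two rows for both visits assume a correlation of 0.5 to 0.8 between the two mean changes.

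**4. The planned between-arm interval.** There are 12 patients and 4 parameters, so 8 residual df. Half-width = t(0.975, 8 df) × residual SD × √(1/6 + 1/6) = 2.306 × 0.577 × SD = 1.33 SD, ignoring covariate imbalance. A residual SD of 4 to 5 gives 5.3 to 6.7 points.

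**5. Cohen's d without an interval.** If d is the between-arm effect size, d = 0.5 with 6 per arm has a 95% interval of −0.66 to 1.64 (noncentral t, 10 df).

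**The case against.** The strongest reply is that this is a feasibility pilot. Section 9.1.1 renounces formal efficacy tests, and its rule only says that a result would suggest a further study. With six patients per arm, the overlaid individual courses show every patient, so the spread is visible. ANCOVA is planned for the follow-up endpoints in the plural, so intervals at Days 7 and 14 can be computed at any time. Naming one visit limits the number of contrasts across many outcomes. The added intervals will also be too wide to settle anything.

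Most of this stands as a reason to rate the point modestly, but it does not close the gap. An interval is estimation rather than a test, and the plan already reports one. It also schedules within-arm paired t-tests for MAIA-2, while the DS-II change that drives the rule gets neither a test nor an interval. Wide intervals are what a reader of the rule needs to see.

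Two stronger readings are tempting, and the documents do not support them.

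- A reader might infer that the visits deciding durability have no interval at all. For the between-arm contrast that is wrong: Day 35 lies beyond 7 days and has one. Of the visits nominally beyond 7 days, only Day 14 lacks it.
- A reader might infer that Day 35 is the wrong visit because the plan itself expects a short-lived effect. The wording behind this, that ketamine "can rapidly and transiently alleviate treatment-resistant unipolar major depression" (Section 1.2) and that a daily oral dose "is well-tolerated and briefly improved depression symptoms" (Section 1.3), describes depression in earlier work. It does not concern DS-II, and it does not concern ketamine with therapy sessions continuing at Days 3 and 11. Section 9.1.1 treats durability as an open question, and the last visit is a reasonable place to look at it.

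**Conclusion.** The point holds in this form: the quantity on which the Section 9.1.1 rule turns, each arm's mean DS-II improvement beyond 7 days, has no planned interval at any visit, and the one planned interval is for a contrast that the rule does not use. Extending the between-arm interval to more visits would help in describing durability but would not by itself supply what the rule needs.

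The size rests on an assumed SD. At 4 to 5 points, the per-arm interval is plus or minus 4.2 to 5.2 points against a 2-point minimum. The half-width equals the minimum only at an SD of 2 / 1.05 = 1.9 points. The calculation takes complete data; the planned filling of missing values with baseline would need to be considered when the intervals are read.

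The plan also leaves open which visit or visits count as beyond 7 days. With the 2-day window, even the Day 7 visit can fall on Day 9. The documents do not settle whether Day 14, Day 35 or both are meant; that is for the sponsor to state. Importance is modest: the trial is descriptive, has 12 patients, and has feasibility as its primary objective.

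**What to change.** In Section 9.2.3, Secondary Objective #2:

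- Report each arm's mean DS-II change from Day 0 (randomization) with a 95% confidence interval at Days 7, 14 and 35, and do the same for the other patient-reported outcomes measured at those visits. State Day 0 as the reference, to match the objective.
- For the ANCOVA difference and its 95% interval, replace at Day 35 by at Days 7, 14 and 35.
- For the clinician ratings (CGI-S, DI, GRID-HAMD-6), give the ANCOVA difference and interval at Days 14 and 35. First reconcile the schedule: the Assessment Plan in Section 6 has these ratings taken immediately before randomization, but the calendar in Section 6.1 marks none at Day 0. Without a Day 0 value, neither a change from randomization nor the planned adjustment for it is possible.

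In Section 9.1.1, state which visit or visits (Day 14, Day 35 or both) define beyond 7 days, and whether the 2-point minimum in the Abstract applies to the rule.

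The cost is one table and a few sentences. No new DS-II data are needed. The sponsor should expect wide intervals and present them as a limit on what the rule can support.

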9.1.2 Randomization

Participants will be randomized 1:1, without stratification, in block sizes of 4.

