9.2 Analyses Plans

9.2.1 Population for Analysis

Descriptive analyses will be prepared based on the Modified Intention-to-Treat study populations, including all participants who received a dose of either oral or intramuscular ketamine on Day 0 (at 0.5 mg/kg).

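### Section 9.2.3 plans Cohen's d with at most six per arm but gives no small-sample correction, contrast, standardizing SD or interval; uncorrected d is biased upward on average, by 8.4% on the usual reading

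*Combined protocol and SAP*

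**What the plan says.** Under Secondary Objective #2, section 9.2.3 plans this analysis for the psychosocial scales: "ANCOVA models of follow-up endpoints as a function of study arm, adjusted for endpoints at baseline and randomization, will be conducted". The results are to be shown as mean trends by arm and as a between-arm mean difference with a 95% CI at Day 35. The plan then adds that "Cohen's d will be calculated at each follow-up time to estimate effect sizes". Follow-up is on Days 7, 14 and 35 for patient-reported outcomes, and on Days 14 and 35 for clinician-rated ones (section 6). Pain and opioid use are to be handled in the same way as DS-II.

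The sample is "12 patients, 6 patients per arm" (abstract). Section 9.1.2 states "Participants will be randomized 1:1, without stratification, in block sizes of 4", and three full blocks of four give exactly six and six. Section 9.2.1 limits the analysis to participants who received ketamine on Day 0, so six per arm is a ceiling.

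For gaps in the data, section 9.2.3 says: "Any missing data will be estimated through the use of single imputation with baseline observations carried forward".

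The plan does not state the contrast behind d, the standardizing SD, any small-sample correction, or an interval for d.

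**The concern.** Cohen's d divides a mean difference by an estimated SD. When that SD rests on few degrees of freedom, the ratio is too large on average, even though the mean difference is unbiased. With six per arm the effect is large enough to show in the first decimal place of a moderate d, and an exact multiplicative correction has long been available.

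The same calculation is repeated many times. Four patient-reported scales at three times, three clinician-rated scales at two times, and pain and opioid use at three times give 4 × 3 + 3 × 2 + 2 × 3 = 24 values of d, counting one score per instrument. With complete data, the bias is away from zero wherever the true effect is non-zero.

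Comparability also suffers. Section 1.1 cites a pre-post d of 0.16 for MaP from a pilot study of 45 patients. If this trial's d were a within-arm pre-post d, a reader might set the two side by side. Their small-sample biases differ (about 1.7% at df 44 against 18.9% at df 5). Because the plan does not define d, a reader could not tell whether the comparison is like with like.

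**Working it through.** The documents give no effect size, power figure or bias figure, so there is no plan figure to reproduce.

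**Inputs.** Six per arm (abstract). An ANCOVA with an intercept, arm and two covariates, the baseline and randomization values (section 9.2.3). The possible degrees of freedom m of the standardizing SD are:
- pooled SD of two arms: 6 + 6 − 2 = 10
- ANCOVA residual SD: 12 − 4 = 8
- SD from one arm: 6 − 1 = 5

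**Formula.** For normal data, E[d]/δ = 1/J(m), where J(m) = Γ(m/2) / [√(m/2) · Γ((m−1)/2)]. Hedges' g is J(m) × d.

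- J(10) = Γ(5)/[√5 · Γ(4.5)] = 24/(2.2361 × 11.6317) = 0.9227
- J(8) = Γ(4)/[2 · Γ(3.5)] = 6/(2 × 3.3234) = 0.9027
- J(5) = Γ(2.5)/[√2.5 · Γ(2)] = 1.3293/1.5811 = 0.8407

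| Standardizing SD | df | J | Average bias, 1/J − 1 | E[d] at true d 0.5 |
|---|---|---|---|---|
| Pooled, between arms | 10 | 0.9227 | +8.4% | 0.542 |
| ANCOVA residual | 8 | 0.9027 | +10.8% | 0.5 × 1.108 = 0.554 |
| One arm only | 5 | 0.8407 | +18.9% | 0.595 |

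The usual approximation 1 − 3/(4m − 1) gives 0.9231 at m = 10 and 0.8421 at m = 5. At m = 44 it gives 1 − 3/175 = 0.9829, a bias of about 1.7%, which is the figure used above for the 45-patient pilot.

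**Bias against sampling error** (noncentral t; the true d of 0.5 is an assumption):
- Between arms: bias 0.042, sampling SD 0.660, ratio 0.042/0.660 = 0.06. The central 95% of observed d runs from −0.69 to 1.94.
- Within one arm: bias 0.095, sampling SD 0.584, ratio 0.095/0.584 = 0.16.
- Over true d from 0 to 1.0, a single between-arm d exceeds its true value 50% to 52% of the time, and a within-arm d 50% to 54%. At a true d of zero the bias is zero.

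**Effect of the correction.** In simulation with complete data (400,000 replicates, true d 0.8), average g/true d was 1.00 at df 10. Since J is below 1, g also varies less: at a true d of 0.5, its between-arm SD is 0.9227 × 0.660 = 0.609.

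**Effect of the planned imputation.** The assumptions are a true between-arm d of 0.8 and a baseline to follow-up correlation of 0.5; the documents give neither. With baseline carried forward for one participant per arm, average d is 0.88 of the true d, and for two per arm 0.69. Multiplying by J(10) takes these to 0.81 and 0.64.

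**The case against.** The strongest reply is that this bias hardly matters in this trial. The primary objective is feasibility. Section 9.1.1 states "No formal power analysis was conducted, and no formal tests of efficacy will be conducted". Its rule for going forward asks for zero treatment-related SAEs and that a dose "demonstrates mean clinical improvement in demoralization assessed by DS-II that endures beyond 7 days post-drug". The abstract sets the minimum improvement at 2 raw DS-II points. None of these is a standardized effect. The bias is also at most about a sixth of one sampling SD in the examples above, and the planned imputation can push d the other way. All of this stands, and it is why the point is minor. It does not justify leaving in a bias that can be removed exactly at no cost. Nor should one rely on two errors of unknown relative size to cancel.

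A second reply is that naming Cohen's d without a formula does not show that no correction will be made. That is fair: the plan is silent, and the point is that it should say.

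Two stronger readings are tempting. A reader might infer that every reported effect size will be 8% to 19% too large. The figures are averages: a single estimate falls below the truth nearly half the time. The upper end also needs an SD from one arm, which the plan does not specify; the d sentence follows the between-arm ANCOVA results, where a pooled SD is the usual choice. A reader might also infer that an inflated d would make the next trial too small. The documents nowhere say that d will size that trial. The between-arm contrast is oral against intramuscular ketamine, both active, whereas section 9.1.1 considers each dose on its own.

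**Conclusion.** The point holds as a minor one. As written, the plan calls for an effect size that cannot be reproduced from its text. If d is left uncorrected, its average upward bias is 8.4% (pooled SD), 10.8% (ANCOVA residual SD) or 18.9% (one arm's SD).

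These figures assume complete, roughly normal data, six per arm and a non-zero true effect. Once baseline values are carried forward, the net bias can be downward, and the correction would then shrink an estimate that is already too small. Hedges' g removes the small-sample bias only; it does not repair the imputation.

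The undefined contrast and SD, and the missing interval, are the larger part of the gap, because sampling error far exceeds the bias. The consequence is confined to descriptive secondary effect sizes and does not reach the feasibility criteria or the go/no-go rule.

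**What to change.** In section 9.2.3, replace the Cohen's d sentence with one that:
- states the contrast (between arms, within arm, or both, labelled separately)
- states the standardizing SD and its degrees of freedom
- reports Hedges' g, that is, d times the exact gamma-function factor for those degrees of freedom (0.923 at df 10, 0.903 at df 8, 0.841 at df 5, recalculated if fewer are analyzed)
- gives a 95% CI for g at each follow-up

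Giving the number of imputed values beside each estimate would let a reader judge how far the imputation may have moved it.

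The cost is a change of wording. Data collection, sample size and conduct are unaffected, and the reported effect sizes become slightly smaller.
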